#### Table I23 **Recommended Granule Dosage of Selumetinib for Co-administration** with Strong or Moderate CYP3A4 and CYP2C19 Inhibitors based on the Initial Proposed Granule Dosing Scheme

Selumetinib dose (mg) bid starting dose a, b without CYP3A4 and CYP2C19 inhibitors	Recommended g selumetinib (mg) fo with strong or mod CYP2C19 inhibitor	granule dosage of or co-administration lerate CYP3A4 and rs (20% reduction) c	Selumetinib granule dosage (mg) reduction for co-administration with strong or moderate CYP3A4 and CYP2C19 inhibitors d					
	AM	PM	AM	PM				
	1	121						

Actual dose in mg administered every 12 hours to achieve exposure approximately **CCI** to capsule in SPRINT; target median AUC = **CCI** ng/mL at selumetinib dose **mg**/m^2 BSA. Sprinkle capsule dose strengths are **mg**, it is recommended that a single sprinkle capsule strength is used to achieve a dose level where possible, to avoid dosing error. b.

c. If the current dosage is up to  $mg/m^2$  bid, reduce to  $mg/m^2$  bid. d. If the current dosage is up to  $mg/m^2$  bid, reduce to  $mg/m^2$  bid. AUC, area under the concentration time curve; bid, twice daily; BSA, body surface area; CYP, cytochrome P450.

#### Table I24 **Recommended Capsule Dosage of Selumetinib for Co-administration** with Strong or Moderate CYP3A4 and CYP2C19 Inhibitors

BSA (m  )	Recommended capsule dosage of selumetinib (mg) for co-administration with strong or moderate CYP3A4 and CYP2C19 inhibitors (20% reduction) a		Selumetinib cap reduction for co-a strong or moder CYP2C19	sule dosage (mg) dministration with ate CYP3A4 and inhibitors b
	AM	PM	AM	PM
1.10 - 1.29	25	25	25	10
1.30 - 1.49	30	25	25	20
1.50 - 1.69	35	30	25	25
1.70 - 1.89	35	35	30	25
≥ 1.90	40	40	30	30

a. If the current dosage is up to 25 mg/m^2 bid, reduce to 20 mg/m^2 bid.

b. If the current dosage is up to  $20 \text{ mg/m}^2$  bid, reduce to  $15 \text{ mg/m}^2$  bid.

bid, twice daily; BSA, body surface area

Changes to, or addition of medications detailed in Table I25 and Table I26 should be avoided, unless clinically indicated. The lists in Table I25 and Table I26 are not intended to be exhaustive, and a similar restriction will apply to other agents that are known to affect CYP2C19, or CYP3A4 activity. Appropriate medical judgment is required. Please contact AstraZeneca with any queries.

СҮР2С19	СУРЗА4	
Strong	Strong	
Fluconazole	Indinavir	
Fluvoxamine	Nelfinavir	
Fluoxetine	Ritonavir	
Ticlopidine	Saquinavir	
Moderate	Cobicistat	
(S)-omeprazole (esomeprazole) high dose 80 mg BD a	Telapravir	
Stiripentol	Itraconazole	
Voriconazole	Ketoconazole	
Triclabendazole	Voriconazole	
Cannabidiol b	Troleandomycin	
Fedratinib	Mifepristone	
Omeprazole	Clarithromycin	
Efavirenz	Lonafarnib	
Moclobemide	Posaconazole	
	Grapefruit juice	
	Conivaptan	
	Tucatinib	
	Ceritinib	
	Nelfinavir	
	Ribociclib	
	Idelalisib	
	Moderate	
	Erythromycin	
	Fluconazole	
	Atazanavir	
	Duvelisib	
	Diltiazem	

# Table I25Inhibitors of CYP2C19 or CYP3A4 that AstraZeneca Recommends not
to be Combined with Selumetinib

CYP2C19	СҮРЗА4
	Dronedarone
	Crizotinib
	Fedratinib
	Letermovir
	Aprepitant
	Lefamulin
	Imatinib
	Verapamil
	Netupitant
	Nilotinib
	Tofisopam
	Berotralstat
	Ciprofloxacin
	Voxelotor
	Isavuconazole
	Cimetidine

a. There is literature evidence for esomeprazole causing weak CYP2C19 inhibition at 20 mg QD and moderate CYP2C19 inhibition at 80 mg QD, between this (eg, 20 mg BD) it is not confirmed at what dose esomeprazole changes from a weak to moderate inhibitor, therefore dose levels > 20 mg QD should be avoided with selumetinib.

b. There is literature evidence for cannabidiol causing moderate CYP2C19 inhibition at doses of 750 mg bid for 7 days. There are no data at what dose cannabidiol becomes a moderate inhibitor, or if lower doses of cannabidiol cause CYP2C19 inhibition.

BD, twice daily; CYP, cytochrome P450; QD, once daily.

# Table I26Inducers of CYP3A4 that AstraZeneca Recommends not to be
Combined with Selumetinib

CYP3A4 Strong	CYP3A4 Moderate	
Rifampin	Efavirenz	
Mitotane	Dabrafenib	
Rifapentine	Cenobamate	
Apalutamide	Bosentan	
Phenytoin	Rifabutin	
Carbamazepine	Lorlatinib	
Enzalutamide	Nafcillin	
Ivosidenib	Phenobarbital	
St John's wort	Modafinil	
Lumacaftor	Pexidartinib	

CYP3A4 Strong	CYP3A4 Moderate	
	Etravirine	
	Elagolix	
	Sotorasib	
	Telotristat ethyl	
	Nevirapine	

CYP, cytochrome P450.

## Appendix J Clinical Outcome Assessments

### J 2

J 3	CCI	
CCI		

J 5

Patient-reported outcomes questionnaire removed due to copyrights

AstraZeneca

### J 6 Palatability Scale

#### **Study Medication Palatability Assessment**

#### **Observer Assessment for Children**

Instructions to carers/parents – Immediately after administration of the selumetinib granule formulation, capture the child's assessment of the taste of the medication.

- 1 Did your child take their study medication this [morning/evening]?
  - Yes (go to Question 3)
  - No (go to Question 2)
- 2 What was the reason for missing the dose?
  - (a) Study doctor/nurse told me to skip the dose (no further questions to be answered).
  - (b) I forgot to give my child the dose (no further questions to be answered).
  - (c) My child did not want to take the dose (go straight to question 4).
  - (d) My child could not swallow the study medication (go straight to question 4).
  - (e) Other (go straight to question 3).
- 3 Choose the response that best matches a description of what you observe of the child's willingness to swallow the study medication.
  - Willingness to Swallow
    - Swallowed without problem
    - Some resistance but did swallow
    - Spit out some/all of medication
    - Vomited up medication
- 4 Was any behaviour observed when the study medication was given to this child that would be indicative of a negative response to the palatability of the study medication? *Palatability is the overall acceptance of the selumetinib granule medicine taken using soft food (as per the Handling Instructions) including taste, flavour, smell, amount of soft food used to take the medicine and texture.* 
  - o Yes
  - o No

If answered Yes, please answer the following questions:

- (a) Did the child turn their head to reject intake of the medication?
  - o Yes
  - o No
- (b) Did the child twist their face or mouth in an expression of displeasure?
  - o Yes
  - o No
- (c) Did the child display any other negative behaviour?
  - o Yes
  - o No

### Handling and Dosing

- 1 Were you able to prepare and dose the granules according to the Handling Instructions?
  - Yes
  - No (go to Question 2)
- 2 If no, please indicate which area/s you had difficulty in following?
  - (a) Difficulty identifying a suitable soft food.
  - (b) Identifying which sprinkle capsules are required for the dose.
  - (c) Opening of sprinkle capsule.
  - (d) Pouring the granules onto a spoon.
  - (e) Pouring the granules into a dosing cup.
  - (f) Adding soft food to the granules.
  - (g) Mixing the soft food with the granules.
  - (h) Giving the granules from a spoon.
  - (i) Giving the granules from a dosing cup.
  - (j) When using a dosing cup, adding further soft food to ensure the whole dose was taken.
  - (k) Giving the whole dose within 30 minutes.
  - (l) Other.

# Appendix K Changes Related to Mitigation of Study Disruptions Due to Cases of Civil Crisis, Natural Disaster, or Public Health Crisis

Note: Changes below should be implemented only during study disruptions due to any of or a combination of civil crisis, natural disaster, or public health crisis (eg, during quarantines and resulting site closures, regional travel restrictions and considerations if site personnel or study participants become infected with SARS-CoV-2 or similar pandemic infection) during which participants may not wish to or may be unable to visit the study site for study visits. These changes should only be implemented if allowable by local/regional guidelines and following notification from the Sponsor and instructions on how to perform these procedures will be provided at the time of implementation.

Please note that during civil crisis, natural disaster, or public health crisis, some study assessments and procedures may not be conducted due to international or local policies or guidelines, hospital or clinic restrictions and other measures implemented to ensure the participant's safety. If in doubt, please contact the AstraZeneca Medical Monitor.

#### **Reconsent of Study Participants During Study Interruptions**

During study interruptions, it may not be possible for the participants to complete study visits and assessments on site and alternative means for carrying out the visits and assessments may be necessary, eg, remote visits. Reconsent should be obtained for the alternative means of carrying out visits and assessments and should be obtained prior to performing the procedures described in Section 8. Local and regional regulations and/or guidelines regarding reconsent of study participants should be checked and followed. Reconsent may be verbal if allowed by local and regional guidelines (note, in the case of verbal reconsent the ICF should be signed at the participant's next contact with the study site). Visiting the study sites for the sole purpose of obtaining reconsent should be avoided.

#### **Rescreening of Participants To Reconfirm Study Eligibility**

Additional rescreening for screen failure due to study disruption can be performed in previously screened participants. The investigator should confirm this with the designated Astra Zeneca Medical Monitor.

In addition, during study disruption there may be a delay between confirming eligibility of a participant and either enrolment into the study or commencing of dosing with study intervention. If this delay is outside the screening window specified in Section 5.4 the participant will need to be rescreened to reconfirm eligibility before commencing study procedures. This will provide another opportunity to re-screen a participant. The procedures detailed in Table 2 must be undertaken to confirm eligibility using the same randomisation number as for the participant.

#### Home or Remote Visit to Replace On-site Visit (where applicable)

A qualified HCP from the study site or TPV service may visit the participants home/or other remote location as per local Standard Operating Procedures, applicable.

Supplies will be provided for a safe and efficient visit. The qualified HCP will be expected to collect information per the CSP.

#### Telemedicine Visit to Replace On-site Visit (where applicable)

In this appendix, the term telemedicine visit refers to remote contact with the participants using telecommunications technology including phone calls, virtual or video visits, and mobile health devices.

During a civil crisis, natural disaster, or public health crisis, on-site visits may be replaced by a telemedicine visit if allowed by local/regional guidelines. Having a telemedicine contact with the participants will allow AEs and concomitant medication to be reported and documented.

#### Data Capture During Telemedicine or Home/Remote Visits

Data collected during telemedicine or home/remote visits will be captured by the qualified HCP from the study site or TPV service in the source documents, or by the participant themselves.

#### Home Delivery of Study Drug by a Designated Courier

If a site visit is not possible, selumetinib may be delivered to the participant's home by a designated courier if feasible. The option of home delivery ensures a participant's safety in cases of a pandemic where participants may be at increased risk by travelling to the site/clinic. This will also minimise interruption of selumetinib administration during other study disruptions, eg, site closures due to natural disaster.

#### **COVID-19** Vaccination

Investigators should follow their local prescribing information and policies when considering if vaccination against COVID-19 is appropriate for their patients participating in an AstraZeneca clinical trial.

Please consider the following if you are considering vaccinating your patient against COVID-19:

For a specific vaccine, consider the potential impact of its relevant prescribing information (i.e., Indications, Contraindications, Warnings and Precautions, Adverse Reactions) on its use in the study population.

For patients with flexibility as to when to be enrolled in an Astra-Zeneca-sponsored study, vaccination prior to first dose of the trial investigational product(s) may be advisable.

Please contact the individual COVID-19 vaccine manufacturer if you have any questions concerning their product.

To better assess the overall impact of COVID-19 vaccination on a particular study and study population, ensure that both the COVID-19 vaccination details (including brand name and manufacturer) is captured in the eCRF as concomitant medication, and adverse reactions are reported.

# Appendix L Abbreviations

Abbreviation or special term	Explanation	
ADR	Adverse drug reaction	
AE	Adverse event	
ALP	Alkaline phosphatase	
ALT	Alanine aminotransferase	
API	Active pharmaceutical ingredient	
AST	Aspartate aminotransferase	
AUC	Area under the concentration-time curve	
AUC0-6	Area under the concentration-time curve from time zero to 6 hours	
AUC0-12	Area under the concentration-time curve from time zero to 12 hours	
AUC0-24	Area under the concentration-time curve from time zero to 24 hours	
AUClast	Area under the concentration-time curve from time zero to the last measurable concentration	
В	Blood	
CCI	CCI	
bid	Twice daily	
BNP	Brain natriuretic protein	
BP	Blood pressure	
BSA	Body surface area	
С	Cycle	
CFR	Code of Federal Regulations	
CI	Confidence interval	
CIOMS	Council for International Organizations of Medical Sciences	
СК	Creatine kinase	
CK-MB	Creatine kinase-myocardial band	
CK-MM	Creatine kinase-muscle	
CLss/F	Apparent total clearance of the drug from plasma at steady state	
CL/F	Apparent total clearance of the drug from plasma	
Cmax	Maximum peak plasma concentration	
COA	Clinical Outcome Assessment	
CONSORT	Consolidated Standards of Reporting Trials	
СРК	Creatine phosphokinase	
CR	Complete response	
CRO	Contract research organisation	
CSP	Clinical study protocol	

Abbreviation or special term	Explanation
CSR	Central serous retinopathy
СТ	Computed tomography
CTCAE	Common Terminology Criteria for Adverse Events
CTIS	Clinical Trials Information System
CV	Coefficient of variation
СҮР	Cytochrome P450
D	Day
CCI	CCI
DES	Data entry site
DCO	Data cut-off
DILI	Drug-induced liver injury
CCI	CCI
ECG	Electrocardiogram
ЕСНО	Echocardiogram
eCRF	Electronic case report form
EDC	Electronic data capture
EEA	European Economic Area
ЕоТ	End of Treatment
ePRO	Electronic patient-reported outcomes
ERK	Extracellular signal-regulated kinase
EU	European Union
FDA	Food and Drug Administration
CCI	CCI
CCI	CCI
FU	Follow-up
GCP	Good Clinical Practice
gCV	Geometric coefficient of variation
CCI	CCI
CCI	CCI
GTPase	Guanosine 5'-triphosphatase
Hb	Haemoglobin
НСР	Health Care Professional
HIPAA	Health Insurance Portability and Accountability Act
HIV	Human Immunodeficiency Virus
HL	Hy's Law

Abbreviation or special term	Explanation	
HLT	High level term	
CCI	CCI	
IATA	International airline transportation association	
IB	Investigator's Brochure	
ICF	Informed consent form	
ICH	International Conference on Harmonisation	
ICR	Independent central review	
IEC	Independent Ethics Committee	
ILD	Interstitial lung disease	
IMP	Investigational medicinal product	
IND	Investigational New Drug	
INR	International normalised ratio	
International co-ordinating Investigator	If a study is conducted in several countries the International Co-ordinating Investigator is the Investigator coordinating the Investigators and/or activities internationally.	
IOP	Intraocular pressure	
IRB	Institutional Review Board	
IRT	Interactive Response Technology	
KM	Kaplan-Meier	
LLN	Lower limit of normal	
LLOQ	Lower limit of quantification	
LVEF	Left ventricular ejection fraction	
LVSD	Left ventricular systolic dysfunction	
Max	Maximum	
MedDRA	Medical Dictionary for Regulatory Activities;	
MEK	Mitogen activated protein kinase	
MEKi	Mitogen activated protein kinase inhibitor	
Min	Minimum	
MPNST	Malignant peripheral nerve sheath tumours	
MRI	Magnetic resonance imaging	
n	Number	
NC	Not calculated	
NCA	Non-compartmental analysis	
NCI	National Cancer Institute	
NEC	Not elsewhere classified	

Abbreviation or special	Explanation	
term		
NF1	Neurofibromatosis type 1	
NIH	National Institutes of Health	
NIMP	Non-investigational medicinal product	
OAT3	Organic ion transporter 3	
ORR	Objective response rate	
Р	Plasma	
P-A	Posterior-anterior	
PBMC	Peripheral blood mononuclear cells	
РВРК	Physiologically based pharmacokinetics	
PD	Progressive disease	
CCI	CCI	
pERK	Phosphorylated extracellular signal-regulated kinase	
CCI	CCI	
PHL	Potential Hy's Law	
РК	Pharmacokinetic(s)	
PN	Plexiform neurofibroma	
РОВ	Pediatric Oncology Branch	
PR	Partial response	
PRO	Patient-Reported Outcomes	
PT	Preferred term	
QTcB	QT interval corrected by Bazett's method	
QTcF	QT interval corrected by Fridericia's method	
Rac	Relative accumulation ratio	
REiNS	Response Evaluation in Neurofibromatosis and Schwannomatosis	
RNA	Ribonucleic acid	
RPED	Retinal Pigment Endothelial Detachment	
RT-PCR	Reverse transcription polymerase chain reaction	
RTSM	Randomisation and Trial Supply Management	
RVO	Retinal vein occlusion	
S	Serum	
SAE	Serious adverse event	
SAP	Statistical Analysis Plan	
SARS-CoV-2	Severe acute respiratory syndrome coronavirus 2	
SD	Standard deviation	
SMQ	Standardised MedDRA query	

Abbreviation or special term	Explanation
SoA	Schedule of Activities
SoC	Standard of care
SRC	Safety Review Committee
SUSAR	Suspected unexpected serious adverse reaction
TBL	Total bilirubin
$t^{1/2}\lambda z$	Elimination half life
tlast	Time to last measurable concentration
tmax	Time to maximum concentration
TPV	Third Party Vendor
CCI	CCI
CCI	CCI
U	Urine
ULN	Upper limit of normal
US	United States
V	Visit
VMI	Visual-Motor Integration
VO 2	Maximal oxygen uptake
Vss/F	Apparent volume of distribution at steady state after non-intravenous administration
Vz/F	Apparent volume of distribution after non-intravenous administration
W	Week
WBC	White blood cell

# Appendix M Protocol Amendment History

The Protocol Amendment Summary of Changes Table for the current amendment is located directly before the Table of Contents.

#### Amendment 3.0 (14 February 2023)

This amendment is considered to be non-substantial based on the criteria set forth in Article 10(a) of Directive 2001/20/EC of the European Parliament and the Council of the European Union and in the EU Clinical Trial Regulation Article 2, 2 (13) as it neither significantly impacts the safety or physical/mental integrity of participants nor the scientific value of the study.

#### **Overall Rationale for the Amendment:**

The main purpose of the amendment is to clarify the requirement that the SRC will evaluate data during the dose finding phase after the first cycle of dosing: i) in '3 (maximum 4) evaluable participants' instead of 'the first 3 evaluable participants', and ii) that if a patient is classed as non-evaluable, additional patients will be dosed to ensure there is a minimum of 3 evaluable participants. Clarifications have been made and other typographical errors have been corrected.

Section Number and Name	Description of Change	Brief Rationale
Overall Design, 6.1.2.2 Definition of an Evaluable Participant for the Dose finding Phase, 9.2 Sample Size Determination	Change to definition of evaluable patient (for both sample size and SRC)	Clarification to existing CSP language
Section 1.3, Schedule of Activities (Table 2)	Foot note z added "Consent can be performed from Day -42. All screening assessments must be performed within 28 days prior to dosing."	To provide flexibility for consenting process
Figure 2 Dose finding phase	Updated flow diagram with "3 evaluable participants" instead of 'Recruit 3 participants' & "continue dosing into cohort" instead of 'continue recruitment into cohort'	To align with the amended wording in Section 6.1.2 (Dose finding phase of the CSP.
Overall design , Section 4.1.2 Overall design	Corrected text from 3 participants to dosing in 3 evaluable participants in Cohort 1	To align with the requirement in section 6.1.2 (Dose finding phase) of the CSP that data from 3 evaluable participants is required

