- x. Adverse events will be collected from the time of signing the informed consent form, throughout the treatment period, and including the follow-up period.
- y. Other systemic NF1-PN targeted treatments will be collected for all participants who discontinue selumetinib until the time when they would have completed 25 cycles of treatment, or they commence an alternative systemic NF1-PN treatment whichever is the earliest.
- z. Consent can be performed on Day -42 onwards. All screening assessments must be performed within 28 days prior to dosing.

CCI	; BSA, body surface area; C, cycle; CSP, Clinical Study Protocol;
D, day; CCI	; ECG, electrocardiogram; EDC, electronic data capture; EoT, end of treatment; CC
CCI	; FU, follow-up; CCI
CCI	LLN, lower limit of normal; LVEF, left ventricular ejection fraction; MRI, magnetic resonance imaging; NF1, neurofibromatosis
type 1; PD, pharmacodynamic	: CC : PK, pharmacokinetic(s): PN, plexiform neurofibroma: SoC, standard of care;

VMI, Visual-Motor Integration; W, week.

AstraZeneca

	Participants receiving selumetinib treatment a			Participants no longer receiving selumetinib treatment		
Procedure b	Every 6 cycles	Every 12 cycles	EoT Safety Follow-up (30 days after last dose)	Every 6 months	Every year	Section or Appendix
Window	±7 days	±7 days	+ 7 days	± 7 days	±7 days	
Full Physical examination	Х		X	Х		8.3.1
Height, weight	Х		X	Х		8.3.2
BSA	Х			Х		8.3.2
Clinical safety laboratory assessments	Х		X	Х		8.3.9
12-lead ECG	Х		Х	If clinically	y indicated	8.3.4
Echocardiogram	Approximately	every 3 cycles	Х	If clinically indicated		8.3.5
Ophthalmology examination		X	Х	If clinically	y indicated	8.3.6
Knee MRI/X-ray (Physeal dysplasia)		X			Х	8.3.7
Performance status	Х		Х	Х		8.3.8
Urinalysis	Х		Х	Х		8.3.9
Vital signs	Х		Х	Х		8.3.3
CI	1	1				
Dispense medication d	To be dispensed	l every 2 cycles				6
Return Medication/Compliance Check		>	Х			6.2 6.4
SAEs and AEs causally related to selumetinib	←======	→	Х	← =======	→	8.4

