  - Intraocular pressure > 21 mmHg (or ULN adjusted by age) or uncontrolled glaucoma (irrespective of IOP). Participants with known glaucoma that is clinically pain-free, has no clinically meaningful vision (light perception only or no light perception) and has increased IOP may be permitted.
  - Participants with any other significant abnormality on ophthalmic examination should be reviewed for potential eligibility.

- Ophthalmological findings secondary to long-standing optic pathway glioma (such as visual loss, optic nerve pallor or strabismus) or longstanding orbito-temporal PN (such as visual loss, strabismus) will NOT be considered a significant abnormality for the purposes of the study.
- 10 Have any unresolved chronic toxicity with CTCAE Grade  $\geq 2$  which are associated with previous therapy for NF1-PN (except hair changes such as alopecia or hair lightening)
- 11 Participants who have previously been treated with a MEKi (including selumetinib) and have had disease progression, or due to toxicity have either discontinued treatment and/or required a dose reduction.
- 12 Have had major surgery within 4 weeks of the first dose of study intervention, with the exception of surgical placement for vascular access. Have planned major surgery during the treatment period.
- 13 Have inadequate haematological function defined as:
  - An absolute neutrophil count  $< 1500/\mu L$
  - Haemoglobin < 9g/dL
  - Platelets <  $100,000/\mu$ L
  - Have had a transfusion (of red cells or other blood derived products) within the 28 days prior to study entry (date of ICF signature).

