## **Prior/Concomitant Therapy**

- 14 Have received or are receiving an IMP or other systemic NF1-PN target treatment (including MEKi) within 4 weeks prior to the first dose of study intervention, or within a period during which the IMP or systemic PN target treatment has not been cleared from the body (eg, a period of 5 'half-lives'), whichever is longer.
- 15 Has received radiotherapy in the 6 weeks prior to start of study intervention or any prior radiotherapy directed at the target or non-target PN.
- 16 Has received growth factors in the 7 days prior to study entry (date of ICF signature).
- 17 Receiving herbal supplements or medications known to be strong or moderate inhibitors of the CYP3A4 and CYP2C19 enzymes or inducers of the CYP3A4 enzyme unless such products can be safely discontinued at least 14 days or 5 half-lives (whichever is longer) before the first dose of study medication.

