#### 6.3 Measures to Minimise Bias: Randomisation and Blinding

The study is open-label and single arm; there is no randomisation.

At screening (Days -28 to -1) the Investigator or suitably trained delegate will:

- 1 Obtain signed informed consent from the legally authorised representative (parent or guardian) of the participant and assent from the participant (if deemed appropriate as per local regulations) before any study specific procedures are performed. Informed consent may be signed within 42 days of dosing window if it is more convenient for the site and families. If laboratory procedures were performed for alternate reasons prior to signing consent, these can be used for screening purposes with consent of the legally authorised representative (parent or guardian) of the participant. However, all screening laboratory and imaging results must have been obtained within 28 days of the first dose of study intervention.
- 2 Obtain a unique 7-digit enrolment number (E-code), through the IRT in the following format PPD

This number is the participant's unique identifier and is used to identify the participant on the eCRFs.

Determine participant eligibility (see Section 5.1 and Section 5.2 for inclusion and exclusion 3 criteria, respectively).

On Day 1, once the participant is confirmed to be eligible, the Investigator, or suitably trained delegate, will:

- 1 Log in to IRT for treatment assignment or registration.
- 2 Participants may be enrolled but not treated. If the participant is not treated, the IRT should be accessed to terminate the participant in the system.
- The IRT will be used to track drug supply. 3
- 4 Participants will begin treatment on Day 1. Participants must not be treated unless all eligibility criteria have been met.

If a participant withdraws from the study, then his/her enrolment code cannot be reused.

Investigators should keep a record (i.e., the participant screening log) of participants who entered screening.

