## Additional Prohibited Concomitant Medication when taking Capsules

Selumetinib capsules contain vitamin E in the form of D- $\alpha$ -tocopheryl polyethylene glycol 1000 succinate, a water-soluble form of vitamin E which acts as a formulation excipient. The maximum daily dose of vitamin E that a study participant may receive from selumetinib is approximately 261.6 mg/day. Therefore, participants should discontinue any supplemental vitamin E at least 7 days prior to transitioning to selumetinib capsules, and should not take any supplemental vitamin E while receiving selumetinib capsules. High doses of vitamin E have been reported to cause bleeding and interfere with blood coagulation processes. Note that this restriction does not apply to participants being treated with the selumetinib granule formulation as it does not contain D- $\alpha$ -tocopheryl polyethylene glycol 1000 succinate.

Selumetinib should be administered with caution in participants who are also receiving concomitant coumarin anticoagulant medications (eg, warfarin). These participants should have their INR monitored/anticoagulant assessments conducted more frequently and the dose of the anticoagulant should be adjusted accordingly.

Prohibited medication/class of drug	Usage (including limits for duration permitted and special situations in which it is allowed)
Other IMP	Not allowed for 4 weeks or 5 half-lives (whichever is longer) prior to the first dose of study intervention.
	Not allowed during the study.
MEK inhibitor	Not allowed for 4 weeks or 5 half-lives (whichever is longer) prior to the first dose of study intervention.
	Not allowed during the study (with the exception of selumetinib study intervention).
Other systemic NF1-PN target treatment	Not allowed for 4 weeks or 5 half-lives (whichever is longer) prior to the first dose of study intervention.
	Not allowed during the study.
Radiotherapy	Not allowed for 6 weeks prior to the start of intervention.
	Radiotherapy (before or during the study) not allowed on target or non-target PNs.
Growth factors	Not allowed within the 7 days prior to study entry (date of ICF signature).
Blood (red cells or other blood derived products) transfusion	Not allowed within the 28 days prior to study entry (date of ICF signature).
Multivitamins containing vitamin E	Must be stopped 7 days prior to initiation of selumetinib capsules.
	Not allowed during the study while being treated with selumetinib capsules.

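### The transfusion and growth-factor exclusions count back from consent rather than from the qualifying blood count, so support given between the two is not excluded; the 42-day consent allowance widens this gap

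*Protocol*

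**What the plan says.** **Consent and sampling.** Protocol Table 2, footnote z: "Consent can be performed on Day -42 onwards. All screening assessments must be performed within 28 days prior to dosing". Section 6.3 agrees: "Informed consent may be signed within 42 days of dosing window if it is more convenient for the site and families", while "all screening laboratory and imaging results must have been obtained within 28 days of the first dose of study intervention". Appendix M (Amendment 3.0) records the added footnote as "Consent can be performed from Day -42. All screening assessments must be performed within 28 days prior to dosing" and gives flexibility in the consent process as the reason.

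**The two look-backs.** Exclusion 13 sets limits for neutrophils (1500/µL), haemoglobin (9 g/dL) and platelets (100,000/µL) and, in the same list, excludes children who "Have had a transfusion (of red cells or other blood derived products) within the 28 days prior to study entry (date of ICF signature". Exclusion 16 reads "Has received growth factors in the 7 days prior to study entry (date of ICF signature". Table 9 in Section 6.5 repeats the consent anchor for both products; its transfusion row says "Not allowed within the 28 days prior to study entry (date of ICF signature". Its rows for other investigational products, MEK inhibitors and other systemic NF1-PN treatment add a ban during the study. The transfusion and growth-factor rows do not.

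**Other washouts.** Major surgery, prior investigational or NF1-PN treatment, radiotherapy, CYP-interacting products and participation in another study all count from the first dose or the start of intervention.

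**Rescreening.** Section 5.4 allows one rescreen after a temporary cause of failure. Appendix A 3 requires no new consent form if this happens within 28 days of the previous signature.

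**Analysis.** SAP Section 3.3.1 takes the last value before the first dose as baseline. Section 4.6.3.2 uses it for haematology change from baseline and for shifts to the worst on-treatment CTCAE grade.

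**The concern.** Exclusion 13 places the transfusion bar beside the blood-count limits. Its evident purpose is to stop a child from meeting those limits only because of a recent transfusion. That works only if the barred period runs up to the blood count. Here it ends at consent, and the blood count may come weeks later.

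A child supported in that interval breaches no criterion. If the support still raises the count at baseline, a later return to the child's own level is recorded as a fall from baseline and possibly as a worse CTCAE grade. Haematology is part of the primary safety endpoint, and a single-arm study has no concurrent control to separate such a fall from a drug effect. Because no rule is broken, the case is not an eligibility deviation, and Table 9 gives no reason to class the product as disallowed.

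**Working it through.** Day -k means k days before the first dose. The plan states no figure for this point, so there is none to reproduce.

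**Inputs:** earliest consent Day -42 (Table 2 footnote z, Section 6.3); sampling window Days -28 to -1 (same places and the Table 2 screening column); look-backs of 28 and 7 days from signature (exclusions 13 and 16, Table 9).

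**Coverage.** Protected window = (consent day - look-back) to consent day. Uncovered days = those strictly between consent and first dose.

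| Consent | Transfusion window | Growth-factor window | Uncovered days | Consent to sample |
|---|---|---|---|---|
| Day -42 | -42 - 28 = -70, to -42 | -42 - 7 = -49, to -42 | -41 to -1 (41) | 14 to 41 days |
| Day -28 | -28 - 28 = -56, to -28 | -28 - 7 = -35, to -28 | -27 to -1 (27) | 0 to 27 days |

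The consent anchor alone leaves 27 days open. The Day -42 allowance adds 41 - 27 = 14. With consent on Day -42, even the earliest permitted sample (Day -28) falls 14 days after protection ends. Whenever the sample falls more than a day after consent, support on the day before it is permitted.

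**A route within the rules.** A child consents on Day -42 and fails on haemoglobin. The child is then supported and rescreened 28 days after signature, on Day -14, under the same consent form. The support falls after study entry, so neither exclusion applies.

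**Alternative anchors.**

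- *Qualifying sample:* the last permitted transfusion is 29 days before the sample and the last permitted growth factor 8 days before. The gap before the sample is closed.
- *First dose, transfusion:* the last permitted day is -29. That is 1, 15 or 28 days before a sample on Day -28, -14 or -1.
- *First dose, growth factor:* the last permitted day is -8. That falls after a sample on Day -28 or -14, so it gives those samples no protection; it is 7 days before a Day -1 sample.

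**Between sample and first dose.** Table 2 footnote f waives the Cycle 1 Day 1 laboratory repeat if tests were done within 14 days and the child's condition is unchanged. Otherwise the repeat, if drawn before dosing, becomes the SAP baseline. Support after the qualifying sample can then raise that baseline. Where there is no repeat, it can prop up early on-treatment values instead. A flag therefore has to run to the first dose.

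**The case against.** A child who has just needed a transfusion is unlikely to be enrolled. Exclusion 4 lets the investigator turn away a child whose condition or laboratory findings threaten safety or the study outcomes, and exclusion 6 covers active bleeding diatheses and uncontrolled disease. Such a child would hardly count as unchanged for the Cycle 1 Day 1 waiver. Medication and procedures are recorded from screening (Section 6.5), so the support would be on file. Protocol Tables 4 and 14 name no haematological toxicity, the safety analysis is descriptive, and Section 8.4.5 makes a laboratory change an adverse event only under stated conditions. The purpose of exclusion 16 is never stated and growth factors are not defined, so the argument is firmer for transfusion. SAP Section 4.3.3 describes all subjects as already included, which suggests that enrolment is complete.

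Much of this stands: it makes the event rare and the priority low, and it limits what a protocol edit can achieve. It does not close the gap. Exclusions 4 and 6 rest on judgement. A repeat sample measures the supported count again. Recording the support leaves the shift tables unchanged.

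A reader might also infer that the Day -42 rule created the problem. It did not: removing it would still leave 27 days open. Nor do the other washouts supply a ready remedy, since counting from the first dose still permits a transfusion the day before a Day -28 sample.

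**Conclusion.** The gap is real in the current text. Neither document bars a transfusion or growth factor between consent and the qualifying blood count. Up to 41 days are uncovered, or 27 when consent is on Day -28. The cause is the consent anchor; early consent enlarges the gap and same-consent rescreening offers a practical way into it.

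The consequence is possible, not shown. It needs a child who received support after consent, was still judged suitable, and was sampled while the support was acting. A reader might infer that baselines are inflated or that haematological toxicity will be misattributed. The documents do not support that: they report no such case and give no frequency of either product, so the effect cannot be sized. It is confined to eligibility on three blood counts and to the haematology summaries; AUC0-12 and ORR are not touched.

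This is a low-priority correction. If enrolment is complete, as the SAP suggests, the analysis check is what remains useful, because haematology is reported at DCO1, DCO2 and DCO3.

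**What to change.** **Protocol, for any further enrolment.** Reconcile Table 2 footnote z and Section 6.3 with exclusions 13 and 16 and Table 9 by counting both look-backs from the qualifying haematology sample instead of the consent date. Their lengths can stay as they are. A first-dose anchor alone is not enough.

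**SAP, Section 4.6.3.** Flag any child given a transfusion from 28 days before the baseline sample, or a growth factor from 7 days before it, up to the first dose. Repeat the haematology shift and change-from-baseline tables without flagged children, or state that there were none. SAP Section 4.1.8.1 classes treatment that stopped before the first dose as prior, so the search must cover prior as well as concomitant medication and procedures. Check that entries reach back to consent, since Section 6.5 starts recording at screening.

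**Cost.** One phrase in two criteria and one table, one derived flag and one repeated set of tables. No new assessments are needed. The downside is an occasional screening delay if recruitment continues.
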